Aim 1A: On the day of surgery, patients will be asked about paresthesia and loss of sensation around the umbilicus. We will document the time when normal sensation returns following the administration of the block. The time elapsed (in minutes) between rectus sheath blockade and the point at which normal sensation returns will be compared between the groups.

Aim 1B: Every 2 hours, we will question the patients regarding their need for pain medication and obtain their Numeric Rating Scale (NRS) pain scores for umbilicus incisional pain. We will document when the patient needs pain medication. The time elapsed (in minutes) from the rectus sheath blockade until the first request for umbilicus pain medication, as well as NRS pain scores will be compared between groups.

Hypothesis:

We hypothesize that rectus sheath injections with the ropivacaine/clonidine combination will be superior in providing long lasting analgesia compared to ropivacaine alone, increasing the duration of sensory block and analgesia, and lowering pain scores at the umbilicus incision.

Aim 2. We will determine if any improvements we observe in pain control satisfaction with the ropivacaine/clonidine combination can be attributed to clonidine's ability to reduce anxiety.

Aim 2A will compare between the two groups patient, parent, and nurse NRS satisfaction scores and correlate them with post-op scores on the state-anxiety component of the State-Trait Anxiety Inventory for Children (STAIC S – Anxiety). Aim 2B will compare postoperative

STAIC S – Anxiety scores between the two groups. Aim 2C will compare within the two groups the difference between the pre and post- op STAIC S Anxiety scores to show if ropivacaine/clonidine is more effective at reducing anxiety.

The methodology will be the following:

Aim 2A: NRS pain control satisfaction scores from patient, parent and nurse will be collected at the completion of the study. State-Trait Anxiety Inventory for Children (STAIC S – Anxiety) questionnaires will be administered to both groups before surgery, and at hour 6 after rectus sheath injections. Post-op anxiety scores in each group will be correlated with satisfaction scores. Aim 2B: The postoperative STAIC S – Anxiety scores will be compared between the 2 groups. Aim 2C: The pre-op STAIC S Anxiety scores will be compared with post- op STAIC S Anxiety within each group.

Hypothesis:

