Based on our experience and preliminary studies, our goal is to treat the patient comprehensively, rather than just the pain itself; whenever possible, we should seek to decrease postoperative anxiety and improve satisfaction with pain control. Recently, we added clonidine to ropivacaine for rectus sheath blockade and noticed longer lasting paresthesia and analgesia (18-22 hours). Because we did not investigate the anxiolytic properties of clonidine, we do not know if the small increase in analgesia we observed is clinically relevant. The potential benefits for patients, families, and medical providers need to be investigated.

Laparoscopic appendectomy is associated with significant pain and anxiety in pediatric populations. The goal of our study is thus to investigate whether the combination of ropivacaine and clonidine is effective in prolonging analgesia beyond the duration observed with ropivacaine alone for pediatric patients undergoing these procedures. Additionally, we will explore the underlying mechanism that may make this combination better equipped for postoperative pain control, so that we can devise more optimal pain control regimens. Our hypothesis is that ropivacaine/clonidine is a significantly better therapeutic regimen for our patients. The primary aim is to determine if the ropivacaine/clonidine combination is superior in providing long-lasting analgesia. The secondary aim is to determine if the ropivacaine/clonidine combination significantly improves satisfaction with pain control due to the psychological benefits of clonidine.

D. RESEARCH DESIGNS AND METHODS

Overview

This is a double blinded prospective study. Following University of Pittsburgh IRB approval, 100 pediatric patients will be recruited. Following parental written consent and patient assent, these patients will be included in the study.

Patient eligibility

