Descriptive statistics will be presented as frequencies (percentages, %) for categorical data or as mean \pm standard deviation (SD) or median and interquartile range for normally or non-normally distributed continuous data, as appropriate. Examination of normal distribution assumption for continuous data will be determined by q-q plots and histograms. Two sample T-Test or Wilcoxon-Mann-Whitney test will be performed to determine differences between groups for normally or non-normally distributed continuous data, respectively. Pearson's chi-square or Fisher's exact test, as appropriate, will be used to compare the frequency distribution of categorical variables between the groups. We will compute Pearson correlation coefficient between NRS pain scores and the anxiety scores. If the assumptions for the parametric test are not met, a nonparametric alternative will be used (i.e. Spearman correlation coefficient).

Sample Size and Power:

The target sample size was calculated with the assumption that the duration of block in the group with ropivacaine only is 720 minutes \pm 288 minutes and in the group with ropivacaine and clonidine the duration is 1080 minutes \pm 432 minutes. The difference would be clinically relevant if the duration of blocks with ropivacaine and clonidine will be at least 50% or more than the duration of blocks with local anesthetic only. Assuming a power of 80%, a level of significance of 0.05, mean and SD as above, only 12 patients would be required in each group. Allowing for a 400% loss arising from patient dropout, unsuccessful block, incomplete follow up because of discharge home on the day of surgery, and inability to determine when paresthesia wears off, we plan to recruit 50 patients in each group, for a total of 100 patients. We estimate that this sample size of 100 patients would provide 80% power to detect a difference as small as 23% in the duration of paresthesia between these 2 groups.

F. SIGNIFICANCE AND APPLICABILITY

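### Aim 1 claims superior analgesia from three outcomes, but none is designated primary and no rule says which result decides the claim

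*Combined protocol and SAP*

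**What the plan says.** Section C states: "The primary aim is to determine if the ropivacaine/clonidine combination is superior in providing long-lasting analgesia". Section B divides this into Aim 1A, the time from block to return of normal sensation at the umbilicus, and Aim 1B, the time to first request for umbilical pain medication together with NRS pain scores. All three are compared between groups. The Aim 1 hypothesis says superiority will show itself by "increasing the duration of sensory block and analgesia, and lowering pain scores at the umbilicus incision".

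Section E assigns a t-test or Wilcoxon test to continuous outcomes. It names no primary endpoint, testing order, multiplicity adjustment or success rule. The only significance level is in the sample-size paragraph ("Assuming a power of 80%, a level of significance of 0.05, mean and SD as above"), and its sidedness is not given. That paragraph ends by claiming "80% power to detect a difference as small as 23% in the duration of paresthesia between these 2 groups". Section G warns that pain scores and analgesic use may be misclassified, and rates numbness as the better marker of how long analgesia lasts.

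**The concern.** An aim is not an endpoint. The claim could rest on numbness, on first request, on NRS pain or on some combination, and the plan does not say which. If numbness shows no difference and first request does, or the reverse, the team would have to decide after seeing the data whether superiority was shown. The 0.05 used for the sample size would then not be the error rate of the primary conclusion.

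Such a split is plausible. The plan's loss allowance goes as far as leaving about 12 evaluable patients per group, partly because the end of numbness may be hard to time. At that number, with the stated SDs, a two-sided t-test on numbness has 63% power.

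**Working it through.** **1. Which outcome does the text point to?**

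| Place | Points to |
|---|---|
| Section C, primary aim | Analgesia. Section B treats duration of analgesia as Aim 1B, separate from numbness (Aim 1A) |
| Section B, Aim 1 hypothesis | All three outcomes, joined by *and* |
| Section E, sample-size inputs | Block duration of 720 and 1080 min, i.e. 12 and 18 hours. Section C gives about 12 hours for analgesia, and 18-22 hours for numbness and analgesia together |
| Section E, last sentence | Numbness |
| Section G, first limitation | Numbness, as a surrogate for analgesia |

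Numbness is the best-supported inference, but it remains an inference.

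**2. The plan's own figure: 12 per group.**

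Inputs from section E: "the duration of block in the group with ropivacaine only is 720 minutes" (SD 288) against 1080 minutes (SD 432), so the difference is 1080 - 720 = 360. The formula is n = 2 x (1.960 + 0.842)^2 x (SD/360)^2 = 15.70 x (SD/360)^2.

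- SD 288 in both groups: 15.70 x 0.64 = 10.05, so 11 by the normal approximation. The exact t-test gives 12 (power 83.3%; 79.6% at 11). The same setting gives a detectable difference of 22.7% at 50 per group, against the stated 23%.
- Both stated SDs: the root mean square of 288 and 432 is 367.1, and 15.70 x 1.040 = 16.3, so 17, or 18 by the t-test.
- One-sided normal approximation with both SDs: 13.

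So 12 is reproduced only by a choice the text does not specify. This does not affect the point here, but it confirms that the calculation concerns one outcome.

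**3. Error of the Aim 1 claim when there is no effect.**

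Assumptions not in the documents: three tests, each two-sided at 0.05, with equal pairwise correlation r. The one related coefficient in section C (0.539) links pain with anxiety, not the Aim 1 outcomes with each other, so r is shown as a range.

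At r = 0:
- any significant difference: 1 - 0.95^3 = 14.3%
- any significant difference favouring clonidine: 1 - 0.975^3 = 7.3%
- all three favouring clonidine: 0.025^3, about 0.002%

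For r above 0, from simulation of three correlated normal statistics (2 million draws):

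| r | Any of three, either direction | Any of three, favouring clonidine | All three, favouring clonidine |
|---|---|---|---|
| 0.3 | 13.6% | 6.8% | 0.04% |
| 0.5 | 12.6% | 6.3% | 0.16% |
| 0.7 | 11.0% | 5.5% | 0.44% |
| 0.9 | 8.4% | 4.2% | 1.1% |
| One test | 5% | 2.5% | 2.5% |

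If the tests were instead one-sided at 0.05, the any-of-three figure favouring clonidine would be 10.3% (r = 0.7) to 14.3% (r = 0), against 5% for one test.

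**4. NRS may be more than one test.**

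Scores are collected every 2 hours and no summary is defined. Purely as an illustration, six time points tested separately would make eight tests: 1 - 0.95^8 = 33.7% in either direction if independent, and less with positive correlation.

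**5. After the change.**

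In a fixed sequence, nothing can be claimed unless the first test succeeds. With no effect on any outcome, the error is therefore 5% (2.5% favouring clonidine), and the sample size does not change. For comparison, Bonferroni (0.05/3 = 0.0167) with the stated SDs needs 22 (normal) or 24 (t) per group for 80% power. At 50 per group, power for numbness is 99.3%, against 99.8% at 0.05.

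**The case against.** The strongest reply is that the plan already has a primary endpoint in all but name. Numbness is the only outcome named in a power statement, and section G ranks it above the pain measures before any data exist. Section D removes patients who cannot time the return of sensation, and takes those discharged while still numb out of the first-aim analysis. Follow-up ends when the block resolves or at discharge. This stands as far as it goes: it is wrong to say that the plan gives no indication. But an implied preference is not a decision rule, and the primary aim's own wording matches Aim 1B.

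A reader might infer that the plan carries an 11% to 14% chance of a false superiority claim. The documents do not support that. They never say that one significant outcome is enough; the hypothesis joins the three with *and*, and if all are required the error falls below that of a single test. With two-sided tests, 11% to 14% also counts results showing clonidine to be worse. The level for each outcome, the sidedness and the correlations are all assumed. The 14% end needs independence, which is unlikely for three measures of the same block at the same site.

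The study also calls itself a pilot. That lowers the stakes, but it still states a superiority hypothesis with an 80% power calculation.

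**Conclusion.** The gap is real and modest. The plan makes a superiority claim with three candidate outcomes, no designated primary and no rule for discordant results, so the deciding outcome could be chosen after the data are seen.

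Its size depends on which reading is taken. Under two-sided 0.05 tests, the chance of a false claim for clonidine is about 5.5% to 7.3% against 2.5% if any one outcome suffices (r from 0.7 down to 0), and under 0.5% over the same range if all three are needed. That the plan leaves both readings open is the defect. None of these figures is an error rate that the plan itself states or implies.

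**What to change.** In Aim 1 and section E:

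1. Name time from block to return of normal sensation as the single primary endpoint, tested two-sided at 0.05.
2. Test time to first umbilical analgesic request next, only if the primary is significant.
3. Then test one pre-defined NRS summary, such as the mean or area under the curve over a fixed window, only if step 2 is significant. Without a defined summary this step cannot be run.
4. Keep Aim 2 as secondary, as section C already has it, and state that it cannot support the primary superiority claim.

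This takes a few lines and no extra patients or data. The cost is that a win on first request or NRS alone can no longer be called superiority. If the sponsor would rather make first request primary, to match the wording of the aim, that outcome should be named and given its own power statement. In either case the choice should be fixed before unblinding.

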The overall hypothesis is that the ropivacaine combined with clonidine administered via single injection ultrasound guided bilateral rectus sheath blocks is a more complete and feasible pain control approach than ropivacaine alone. We will test this hypothesis by pursuing the following specific aims: 1) determine if the ropivacaine/ clonidine combination is superior in providing long-lasting analgesia to ropivacaine alone; and 2) advance the understanding of ropivacaine/ clonidine rectus sheath blockade, and determine if this combination significantly improves satisfaction with pain control due to psychological benefits of clonidine.

We view this innovative study as a first step in developing an evidence-based therapeutic pain regimen for laparoscopic appendectomy. Every hour of effective analgesia counts, as it improves quality of care and reduces health care costs. Upon successful completion of this project, we will seek further support to prospectively validate this combination for other trunk blocks as well as various surgical procedures. The safety of ropivacaine/clonidine blockade should be evaluated in large scale prospective studies.

B. SPECIFIC AIMS AND METHODS TO BE EMPLOYED

Laparoscopic appendectomy is a popular and minimally invasive technique used for removing the appendix, but it is associated with significant pain and anxiety in pediatric populations. The goal of this pilot study is to examine whether ropivacaine/clonidine is effective at prolonging analgesia beyond the effects of ropivacaine alone and to investigate the underlying mechanism (i.e. anxiety reduction) that may make this combination better suited for postoperative pain control, so that better therapeutic regimens can be offered to our patients. The overall hypothesis is that the ropivacaine /clonidine rectus sheath blockade is a more complete and feasible pain control approach after laparoscopic appendectomy. This hypothesis will be tested by the following specific aims:

Aim 1. To determine if the ropivacaine/clonidine combination can prolong analgesia, we will determine if ropivacaine/clonidine rectus sheath blockade is superior in providing long-lasting analgesia compared to ropivacaine alone. Aim 1A will compare duration of paresthesia at the umbilicus instrument site. Aim 1B will compare duration of analgesia at the same location.

The methodology will be the following:

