We hypothesize that patients, parents and nurses will experience more pain control satisfaction with the ropivacaine/clonidine combination than with the ropivacaine alone, not only because the combination will provide longer lasting analgesia, but also because clonidine's power to reduce anxiety will lead to a concomitant decrease in pain.

C. BACKGROUND

Appendectomy is one of the most common emergency surgeries performed in children, especially in adolescents and teens. (1) At present, the laparoscopic technique has become a popular approach for performing appendectomies, (1) as it is minimally invasive and has been shown to improve patients' outcomes. (2). Despite these advantages, children often experience significant pain (3) and anxiety during these laparoscopic procedures that extends after the day of surgery, particularly those who are particularly anxious before surgery. Indeed, children who are highly anxious prior to surgery tend to have more postoperative pain, delayed hospital discharge, higher incidence of emergence delirium, sleep disturbances, and other maladaptive behavior changes that can last up to a few weeks following surgery. (4), (5)

Effective postoperative analgesia after laparoscopic appendectomy is necessary for optimal recovery. (3) By simultaneously improving analgesia and reducing side-effects from opioid use, a multimodal approach that includes peripheral nerve blocks—a form of regional analgesia—could form the crux of an effective pain control regimen for patients undergoing laparoscopic appendectomy. Despite the promise of such an approach, finding a nerve block that is suitable for patients undergoing laparoscopic appendectomies is challenging. Nerve blocks typically consist of local anesthetic alone, and it is difficult to find a local anesthetic with both minimal side effects and ability to combat pain and anxiety for extended periods of time. For instance, even though single injection nerve blocks (such as rectus sheath blocks) in combination with multimodal analgesia for laparoscopic appendectomy are helpful and minimally invasive, they do not last over the course of the most painful part of postoperative period, the first 24 hours. (6) By contrast, continuous peripheral nerve blocks can provide enduring analgesia, but they are costly and deemed excessively invasive in the context of this minimally invasive surgery.

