Minimal sedation can be desired for some pediatric patients that underwent surgeries. Clonidine produces effective sedation for patients on mechanical ventilation that can be uncomfortable because anxiety, pain and endotracheal intubation. (21) Clonidine at 2 mcg/kg prevents sevoflurane-induced agitation (22), (23) and can be used as premedication in children. (24), (25) Oral clonidine can relieve postoperative anxiety, and subsequently improve pain control. (26) No studies have investigated its role as an anxiolytic when added to local anesthetic for a nerve block.

Preliminary studies:

The Children's Hospital of Pittsburgh of University of Pittsburgh Medical Center (CHP of UPMC) has a dedicated service that performs peripheral nerve blocks on a regular basis. Over the last academic year, 190 patients (10-17 years old, 126 patients) that underwent laparoscopic appendectomy had peripheral nerve blocks (rectus sheath and transversus abdominis plane). Our experience suggests that children localized the majority of their pain to the umbilicus instrument site. (6) To treat this pain is crucial, as this pain interferes with eating, bedside activities and ambulation, and can delay discharge.

Our preliminary study (retrospective chart of 50 patients that underwent laparoscopic appendectomy) demonstrates that rectus sheath blocks, which target pain at the umbilicus instrument, are as effective as a combination of transversus abdominis plane and rectus sheath blocks, which target pain at all instrument sites. This is an important finding, as it means that instead of dividing the amount of local anesthetic delivered between four sites,

more anesthetic can be delivered bilaterally to a single location. This can result in analgesia that lasts around 12 hours, which is relatively short for our purposes but still an improvement.

[name] prospective study demonstrates that postoperative pain scores after laparoscopic appendectomies correlate very well with postoperative anxiety (Pearson coefficient =0.539;133 subjects, 11-17 years old). Patients that received regional anesthesia for laparoscopic surgeries reported less anxiety after surgery (Spearman coefficient = -0.143, $p = 0.042$; pending publication; 202 subjects, 11-17 years old). The use of single injection nerve blocks predicts less postoperative pain ($p=0.04$), better mood ($p=0.009$), less catastrophizing thoughts about pain ($p=0.007$).

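### Aim 2C tests anxiety change within each arm although its question is between arms, and the Aim 2A correlation cannot show that satisfaction gains come from reduced anxiety

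*Combined protocol and SAP*

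**What the plan says.** Section B gives Aim 2C a comparative purpose: to examine "the difference between the pre and post- op STAIC S Anxiety scores to show if ropivacaine/clonidine is more effective at reducing anxiety". The method given for it is "The pre-op STAIC S Anxiety scores will be compared with post- op STAIC S Anxiety within each group".

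Aim 2B compares postoperative STAIC-S between the two arms and makes no use of the preoperative score. For Aim 2A, satisfaction is compared between arms, and "Post-op anxiety scores in each group will be correlated with satisfaction scores".

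The objective above these sub-aims is causal: "We will determine if any improvements we observe in pain control satisfaction with the ropivacaine/clonidine combination can be attributed to" clonidine's effect on anxiety. The opening summary puts it as "determine if this combination significantly improves satisfaction with pain control due to psychological benefits of clonidine", and the statement of the secondary aim at the end of Section C says much the same.

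Section E names two-sample tests for continuous data, tests for categorical data, and a correlation of NRS pain with anxiety. It names no paired test, change-score analysis, ANCOVA or mediation analysis, and it does not list the anxiety–satisfaction correlation. Section G accepts that preoperative anxiety may carry over into postoperative scores and relies on a pre/post comparison to deal with this.

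**The concern.** Whether one treatment reduces anxiety more than another is a question about the difference between arms. A test of change in each arm asks whether that arm's mean moved from baseline. One arm can reach significance and the other miss it when the true changes are equal, and both can reach it when the true changes differ. State anxiety may well change after surgery in both arms whatever the block contains, so neither situation is far-fetched.

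The pre/post comparison that Section G relies on is, as written, this within-arm one. It does not adjust the arm difference for preoperative anxiety.

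The attribution question is separate. The Aim 2 hypothesis gives two routes to satisfaction. One is analgesia that lasts longer. The other is anxiolysis, where the drug's "power to reduce anxiety will lead to a concomitant decrease in pain". Section C reports that "postoperative pain scores after laparoscopic appendectomies correlate very well with postoperative anxiety" (Pearson 0.539). A correlation computed inside each arm contains no treatment contrast and no control for analgesia, so it cannot separate the routes. At stake is the mechanistic claim that the plan makes part of its goal.

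**Working it through.** **Inputs.** From the documents: 50 patients recruited per arm, significance level 0.05 (taken as two-sided), 12 per arm as the calculated requirement for block duration, and pain–anxiety r = 0.539. The documents give no STAIC-S mean, SD, expected change or pre/post correlation, no pain–satisfaction correlation and no decision rule for Aim 2C. These are assumed below and varied. There is no Aim 2 power figure to reproduce.

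**1. Same true change in both arms.** Take as the rule a significant fall with clonidine and no significant change with ropivacaine. Let p be the probability of a significant fall in one arm (paired t-test, noncentral t, noncentrality = change × √n, change in SDs of the change score). The arms are independent, so the rule is met with probability p × (1 − probability of significance in either direction), which is close to p(1 − p). For n = 50:

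| Common change (SD) | p | Rule met |
|---|---|---|
| 0 | 0.025 | 2% |
| 0.1 | 0.103 | 9% |
| 0.2 | 0.283 | 20% |
| 0.28 | 0.492 | 25% |
| 0.4 | 0.792 | 16% |
| 0.5 | 0.934 | 6% |
| 0.8 | 0.9998 | 0.02% |

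The ceiling is 0.5 × 0.5 = 25% for any n. Only its location moves: 0.41 SD at 25 per arm and 0.62 SD at 12. A valid between-arm test would favour clonidine in 2.5% of trials. In a simulation of 6,000 trials at 0.28 SD and 50 per arm, the rule gave 23.9%, ANCOVA 2.2%, rank-based ANCOVA 2.3% and the post-only test 2.5%.

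**2. A real difference.** Assume falls of 0.5 SD (ropivacaine) and 1.0 SD (clonidine) and a pre/post correlation of 0.5, so that the SD of the change equals the SD of the score.

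| Per arm | Both arms significant | Rule credits clonidine | Aim 2B power | ANCOVA power |
|---|---|---|---|---|
| 50 | 93% | 7% | 70% | 82% |
| 25 | 67% | 33% | 41% | 52% |
| 12 | 31% | 57% | 22% | 27% |

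With fewer patients the rule credits clonidine more often, because the ropivacaine test then fails for lack of power. That says nothing about the difference between arms.

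**3. Precision of a between-arm test.** The difference detectable with 80% power (two-sample t) is 0.57 SD at 50 per arm, 0.81 at 25 and 1.20 at 12. ANCOVA multiplies this by √(1 − ρ²), where ρ is the pre/post correlation. For ρ = 0.3, 0.5 and 0.7 the variance falls by 9%, 25% and 49%:

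- 50 per arm: 0.54, 0.49, 0.40 SD
- 25 per arm: 0.77, 0.70, 0.58 SD

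**4. What the Aim 2A correlation can show.** Suppose first that anxiety drives pain and pain drives satisfaction. Then suppose that pain drives both anxiety and satisfaction. In each case r(anxiety, satisfaction) = r(pain, anxiety) × r(pain, satisfaction). With an assumed pain–satisfaction r:

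- −0.3: 0.539 × −0.3 = −0.16, significant in 20% of 50-patient arms
- −0.5: 0.539 × −0.5 = −0.27, significant in 47%
- −0.7: 0.539 × −0.7 = −0.38, significant in 78%

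The percentages are Fisher z power and are identical under both causal directions. They are not rates of wrong attribution; they show that the statistic does not discriminate.

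**The case against.** - **The intent may have been between-arm.** The introduction to Aim 2C speaks of the pre/post difference and of greater effectiveness, and Section E names only between-group tests for continuous data. A two-sample test of change scores is a plausible reading. This stands as a statement of intent, but the method sentence says otherwise and Section E never mentions change scores. On either reading the analysis is not specified.
- **Aim 2B already compares anxiety between randomised arms.** It does, and validly. Under randomisation, leaving out the preoperative score costs precision and does not bias the comparison. The size of the ANCOVA gain rests on correlations the documents do not give. This limits the severity, but it does not give Aim 2C a valid test.
- **The 25% is a worst case under a rule nobody wrote down.** Correct: it falls to 6% at 0.5 SD and 0.02% at 0.8 SD. The miss case also weakens with fewer analysed patients (33% against 41% for Aim 2B at 25 per arm). Since the plan allows for heavy losses, 50 per arm is an upper limit. The mismatch between question and method does not depend on these figures.
- **The product formula assumes no direct path from anxiety to satisfaction.** With an assumed direct standardised path of −0.3 and total pain–satisfaction r of −0.5, the pain coefficient is −0.5 + 0.3 × 0.539 = −0.338, and the anxiety–satisfaction correlation is −0.3 − 0.338 × 0.539 = −0.48 instead of −0.27. The value changes. It is still the same whichever of pain and anxiety comes first, when the same direct path is added to both models.

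**Conclusion.** The concern holds. As written, Aim 2C does not test its own question, no planned arm comparison uses the preoperative STAIC-S score, and the Aim 2A correlation cannot support attribution to anxiolysis. These conclusions follow from the text alone.

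The numerical consequences are conditional on an assumed decision rule and assumed STAIC-S effects. At 50 per arm they are up to 25% spurious clonidine-only findings when the arms change equally, and 7% recognition of an assumed 0.5 SD advantage that Aim 2B would detect with 70% power and ANCOVA with 82%.

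This concerns the secondary aim of a pilot. The primary aim and the sample size are untouched, and Aim 2B leaves a valid test of the effect on anxiety. The change should be made, but the trial does not stand or fall on it.

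**What to change.** 1. **Aims 2B and 2C (Section B):** replace the within-arm test and the unadjusted postoperative comparison with one between-arm ANCOVA of postoperative STAIC-S on arm, adjusted for preoperative STAIC-S. Report the adjusted difference with its 95% CI. If the residuals fail the normality check that Section E describes, use a rank-based ANCOVA. Show within-arm changes descriptively only.
2. **Section E:** list this ANCOVA. Also list the anxiety–satisfaction correlation and reconcile it with the pain–anxiety correlation, which is the only one named there now.
3. **Section G:** cite the ANCOVA as the way preoperative anxiety is handled.
4. **Aim 2A:** keep the between-arm satisfaction comparison and label the correlation exploratory.
5. **Causal wording (opening summary, Aim 2, secondary aim in Section C):** restate the objective as comparing satisfaction between arms and exploring whether satisfaction is associated with postoperative anxiety. The Aim 2 hypothesis may keep its two proposed routes if it says that this design does not separate them.

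The cost is wording only. Section D already schedules STAIC-S before surgery and 6 hours after the block, so no further data or patients are needed.
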